9.4.3. Efficacy Analyses

Efficacy data will be summarized and analyzed in the ITT population.

The key sUA efficacy endpoint (proportion of subjects with sUA <6.0 mg/dL at Month 6) will be summarized descriptively by treatment group and a comparison of the response rates will be presented using the CMH test statistic, stratified by type of XOI, Baseline measurable target tophus status (present/absent), and Screening eCrCl (30.0 to <45.0 mL/min or 45.0 to <60.0 mL/min), as appropriate as stated in [Section 9.1](#). Results will be expressed as proportions, corresponding adjusted 95% CI of the difference between response rates, and p-values. Subjects who are missing their Month 6 sUA results will be analyzed as non-responders.

The LESU + XOI group will be deemed superior compared with the PBO + XOI group if there is sufficient statistical evidence to reject the following null hypothesis:

H₀: $p_1 = p_2$ ie, no evidence that the proportion of subjects achieving an sUA response by Month 6 in the LESU + XOI group is different from the PBO + XOI group.

and in favor of the alternative hypothesis:

H₁: $p_1 \neq p_2$ ie, the proportion of subjects achieving an sUA response by Month 6 in the LESU + XOI group is different from the PBO + XOI group.

The key efficacy endpoint will be tested in the overall study population as well as the subset of subjects whose Screening eCrCl is 30.0 to <45.0 mL/min. To account for multiplicity, a hierarchical testing procedure will be performed to preserve an overall alpha at 0.05 level. First, the null hypothesis for the key efficacy endpoint will be tested in the overall population at an alpha level of 0.05. If the null hypothesis is not rejected, the testing will be stopped. Otherwise, the endpoint will then be tested in the subset of subjects whose screening eCrCl is 30.0 to <45.0 mL/min at an alpha level of 0.05.

Sensitivity analyses (eg, observed cases or other imputation approaches) will be explored to assess the impact of missing data (details provided in the SAP).

Absolute and percent change from Baseline in sUA concentration will be summarized by visit and analyzed using MMRM that includes terms for treatment (LESU + XOI and PBO + XOI), visit, treatment by visit interaction, stratification factors (type of XOI [allopurinol or febuxostat], Baseline measurable target tophi status [present/absent], and Screening eCrCl [30.0 to <45.0 mL/min or 45.0 to <60.0 mL/min], as appropriate as stated in [Section 9.1](#)), and Baseline sUA as covariates. The model will assume an unstructured covariance matrix. If convergence issues are encountered, alternative covariance structure will be explored (details will be provided in SAP). LS mean by treatment and LS mean difference between LESU + XOI and PBO + XOI alone will be estimated from the MMRM analysis, along with the 95% CI of LS mean difference.

The proportion of subjects reaching sUA <6.0 mg/dL at each visit will also be presented. Additional efficacy analyses to support the key efficacy endpoint will include the proportion of subjects reaching sUA <6.0 mg/dL at multiple consecutive visits (eg, Months 3 and 6). CMH estimates of 95% CI for difference will also be presented.

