4. STUDY POPULATION SELECTION

4.1. Study Population

Approximately 600 subjects will be enrolled (300 per treatment group).

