9.1. General Considerations

All subjects will be randomized to either lesinurad 200 mg or matching placebo in combination with an XOI in a 1:1 ratio and stratified by the following stratification factors:

- Screening eCrCl: the average eCrCl of Screening Visit 1 and Screening Visit 2 (30.0 to <45.0 mL/min or 45.0 to <60.0 mL/min).
- Baseline measurable target tophus status: present or absent.
- Type of XOI: allopurinol or febuxostat.

This study will enroll approximately 50% of subjects with eCrCl 30.0 to <45.0 mL/min and approximately 50% with eCrCl 45.0 to <60.0 mL/min. There is no planned sample size requirement on the number of subjects enrolled by type of XOI or Baseline tophus status. However, a stratification variable (eg, Baseline measurable target tophus status [present/absent]) may be dropped from the stratified analysis (eg, mixed model repeated measures [MMRM] or Cochran Mantel Haenszel [CMH]) if the number of subjects in any stratum is very low (eg, <10% of total subjects). The decision to drop a stratification variable will be made prior to database lock and will be documented in the SAP.

All safety and efficacy data will be listed and summarized by treatment group.

Baseline is defined as the last observed measurement prior to the first dose of IP, unless otherwise specified.

Descriptive statistics will consist of the number of subjects (n), mean, standard deviation (SD), median, minimum, and maximum for continuous variables, and counts and percentages for categorical variables.

Unless otherwise specified, all confidence intervals (CIs) will be calculated at the 95% level and all hypothesis tests will be performed at the 0.05 level. All analyses including summaries and listings will be performed using SAS[®] software version 9.1 or higher.

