9.2. Determination of Sample Size

Approximately 600 subjects will be randomized 1:1 to either the lesinurad (LESU) + XOI or placebo (PBO) + XOI group in this study.

For safety endpoint analyses, this sample size provides sufficient precision around the estimated between-treatment difference for the absolute and percent changes in eCrCl from Baseline to Month 24 based on the normal distribution CI with 95% two-sided confidence level. For the difference in absolute change from Baseline to Month 24, the estimated precision is ± 1.6 mL/min assuming a common SD for the change from Baseline in each treatment group of 10 mL/min estimated from the lesinurad Phase 3 development program. For the difference in percent change from Baseline to Month 24, the estimated precision is $\pm 3.2\%$ assuming a common SD for the

percent change from Baseline in each treatment group of 20% estimated from the lesinurad Phase 3 development program.

For the key efficacy endpoint analyses, this sample size will provide >90% power for the overall population and >80% power within each Screening eCrCl stratum to detect a treatment difference for the proportion of subjects achieving sUA <6.0 mg/dL at Month 6 of 15% (20% in the PBO + XOI group versus 35% in the LESU + XOI group, as estimated from the lesinurad Phase 3 development program), using a binomial distribution at an alpha of 0.05 (two-sided). Based on the assumptions above, this sample size provides sufficient precision such that the minimum statistically significant difference in response rate is approximately 10% in the overall population, and approximately 11% in the Screening eCrCl 30.0 to <45.0 mL/min stratum, at the two-sided 5% level.

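### Adjusting the key sUA responder test for Baseline sUA would add roughly 1 to 6 points of power in the 30.0 to <45.0 mL/min subset; the planned CMH test is valid without it

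*Combined protocol and SAP*

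**What the plan says.** Section 9.4.3 makes the key efficacy comparison a CMH test, "presented using the CMH test statistic, stratified by type of XOI, Baseline measurable target tophus status (present/absent), and Screening eCrCl", with an adjusted 95% CI for the difference in response rates. A missing Month 6 value counts as non-response. The test is run first in all subjects and then, if significant, in those with Screening eCrCl 30.0 to <45.0 mL/min, each at 0.05. The sensitivity analyses named there concern missing data only.

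The MMRM for change in sUA, in the same section, has treatment, visit, their interaction, the stratification factors and "Baseline sUA as covariates".

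Section 9.2 claims ">90% power for the overall population and >80% power within each Screening eCrCl stratum", for "20% in the PBO + XOI group versus 35% in the LESU + XOI group", "using a binomial distribution at an alpha of 0.05 (two-sided)". Section 4.1 gives the size: "Approximately 600 subjects will be enrolled (300 per treatment group)". Section 9.1 plans about half of the subjects in each eCrCl stratum and lets a stratification factor be dropped when one of its levels is very small.

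Uric acid belongs to Analytes 1 (Table 1), drawn at both Screening Visits and at the Baseline Visit (Sections 8.1.1 to 8.1.3). Dosing starts the next day. Inclusion criterion 7 requires sUA of at least 6.0 mg/dL at both Screening Visits and sets no upper limit.

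**The concern.** The endpoint is whether a subject crosses a fixed cut-off on the same analyte that is measured at Baseline. Starting distance from the cut-off varies between subjects, and the XOI dose is meant to stay stable, so Baseline sUA is likely to predict response. A test that ignores a prognostic baseline measure leaves explainable variance in the treatment comparison.

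This matters most in the second step of the hierarchy. There Screening eCrCl is constant, so the CMH has at most XOI type and tophus status to stratify on, and Section 9.1 allows either to go. That step also has the smaller sample and the thinner power reserve. Section 9.2 states no allowance for missing Month 6 values, which count against response.

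**Working it through.** **Inputs from the protocol.** Rates 20% and 35%, two-sided alpha 0.05 and 300 per arm (Sections 4.1 and 9.2); 1:1 allocation and about 50% per eCrCl stratum (Section 9.1), hence about 150 per arm in the subset.

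**Step 1: reproduce the stated power.** With pooled variance under the null, power = Φ{[0.15√n − 1.96√(2 × 0.275 × 0.725)] / √(0.20 × 0.80 + 0.35 × 0.65)}.

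- Subset, n = 150: (1.8371 − 1.2377) / 0.6225 = 0.963, power 83.2%. Exact enumeration of the Pearson test gives 83.5% and Fisher's exact test 80.3%. Only the continuity-corrected version falls just short of 80%, at 79.7%.
- Overall, n = 300: (2.5981 − 1.2377) / 0.6225 = 2.185, power 98.6%.

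Both stated figures hold.

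**Step 2: convert variance removed into power.** If adjustment removes a share r of the variance of the risk difference, the effective size per arm is n/(1 − r).

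| r | Subset effective n | Subset power | Overall power |
|---|---|---|---|
| 0 | 150.0 | 83.2% | 98.6% |
| 5% | 157.9 | 85.1% | 98.9% |
| 10% | 166.7 | 86.9% | 99.2% |
| 15% | 176.5 | 88.7% | 99.4% |
| 20% | 187.5 | 90.5% | 99.6% |

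**Step 3: link r to the correlation, by simulation.** The protocol gives neither the within-arm correlation ρ of Baseline with Month 6 sUA nor the spread of Baseline sUA. Both are assumed. Baseline sUA was drawn from a normal distribution truncated at 6.0 mg/dL, and response rates were fixed at 20% and 35% with 150 per arm. Simulation A assumed a Baseline SD of about 0.9 mg/dL after truncation and 25% prevalence each of febuxostat and tophi, with 4,000 runs per setting (Monte Carlo SE about 0.6 points). Simulation B is a separate run on the same design. Each cell shows planned CMH versus adjusted risk difference.

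| ρ | Simulation A | Simulation B |
|---|---|---|
| 0 | 84% vs 84% | 83% vs 83% |
| 0.2 | 83% vs 85% | 84% vs 85% |
| 0.3 | 83% vs 86% | 83% vs 86% |
| 0.4 | 81% vs 85% | 82% vs 86% |
| 0.5 | 83% vs 88% | 84% vs 89% |
| 0.6 | 84% vs 90% | 84% vs 90% |

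Cross-check at ρ = 0.5 in A: the empirical SE fell from 0.0502 to 0.0471, so r = 1 − (0.0471/0.0502)² ≈ 0.12. Effective n is 150/0.88 = 170.5, giving 87.7% by the Step 1 formula, in line with the simulated 88%.

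**Step 4: type I error.** With 20% in both arms and ρ = 0.5, A gave 5.1% for CMH and 5.5% adjusted (SE about 0.35 points). B, with influence-function standard errors, gave 5.0% adjusted. Further null runs of 20,000 gave 5.1-5.5% adjusted against 4.8-5.3% for CMH.

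**Step 5: missing Month 6 values.** If 20% and 35% are rates among subjects with data (an assumption), 10% missing gives 18% versus 31.5% and subset power of 77.6%; 5% and 15% missing give 80.5% and 74.4%. In A with 10% missing, CMH had 77-79% power. The adjusted test had 80% and 83% at ρ = 0.3 and 0.5.

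**The case against.** The strongest reply is that nothing is broken. The CMH matches the randomization strata, gives an adjusted CI and meets the plan's own power target. All of that stands. A reader might infer that the plan is underpowered or contradicts itself by using Baseline sUA in one model and not the other. The documents support neither reading: the stated power reproduces, and the MMRM analyzes change from Baseline, a different endpoint.

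The stakes are also modest. The primary objective is safety, and this is the second step of an efficacy hierarchy. A reader might expect adjustment to help both steps. It does so only nominally: the overall test moves from 98.6% to at most 99.6% in the range shown.

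The size of the gain is assumed. A simulation that ignores the entry rule and compares with an unstratified chi-square shows 88%, 89% and 91% at ρ = 0.4, 0.5 and 0.6. Those figures should not be used, because the planned comparator is the stratified CMH and entry is restricted to sUA of at least 6.0 mg/dL. Simulation A also has limits. Its stratification factors carry no prognostic information, so if XOI type or tophus status predicts response, CMH already captures part of the gain. The Baseline Visit value itself is not bounded at 6.0 mg/dL, so truncation there is an approximation.

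Nor is adjustment wholly free. A test run at 5.5% instead of 5.0% gains about 1 point by itself: (1.8371 − 1.919 × 0.6315) / 0.6225 = 1.005, power 84.2% against 83.2%. At ρ = 0.2 the gain cannot be told apart from that effect. At 0.4 and above it clearly exceeds it.

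Finally, Section 9 defers detail to a SAP whose separate text was not available here, so a supportive adjusted analysis there cannot be ruled out. Section 9.4.3 does fix the CMH as the key test.

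**Conclusion.** The point holds as an improvement worth making. The key test leaves out a pre-dose covariate that the trial already collects and that probably predicts response. In the 30.0 to <45.0 mL/min test, adjustment would raise power from about 83% to roughly 85-90%, a gain of about 1 to 6 points for assumed correlations of 0.2 to 0.6. At zero correlation nothing is lost. In the overall test the gain is negligible.

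The direction follows from the endpoint being a cut-off on the same analyte. The size rests on an assumed correlation and Baseline distribution, and on the plan's 20% and 35%. The missing-data figures rest on the further assumption that those rates apply to subjects with data.

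**What to change.** Before unblinding, amend Section 9.4.3 or the SAP as follows.

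- Make the key comparison a standardized (marginal) risk difference with its 95% CI and p-value, from a logistic model with treatment, continuous Baseline sUA and the stratification factors. This keeps the difference in proportions that the plan already reports; a logistic odds ratio would not.
- Use all three factors in the overall test. In the 30.0 to <45.0 mL/min test use only XOI type and tophus status, since Screening eCrCl is constant there. Apply the Section 9.1 rule for sparse factors to both models.
- Name a robust (influence-function or sandwich) variance estimator with a small-sample degrees-of-freedom correction.
- Leave the endpoint, the hierarchy, the alpha levels and non-responder imputation unchanged, and keep the stratified CMH as a sensitivity analysis.

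The sponsor could check the correlation in its Phase 3 data, the stated source of the planning rates. Staying with CMH and adding a median split of Baseline sUA as a stratum recovers only part of the gain (86% against 88% at ρ = 0.5 in simulation A).

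The cost is wording, with no new data or subjects. The downside is that the p-value becomes model-based and holds the 5% level only as well as the chosen variance estimator does, so the estimator has to be fixed in advance.

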9.4.4. Exploratory Endpoints

For all exploratory endpoints, descriptive statistics will be provided at each scheduled visit.

For percent change from Baseline in the sum of target tophi area among subjects with target tophus at Baseline, the between-treatment difference will be assessed using similar MMRM analysis as appropriate as in [Section 9.4.2.1](#).

For the proportion of subjects with target tophi at Baseline who experience complete resolution of at least 1 target tophus at any time during study, the between-treatment difference in tophus resolution rates in this subset of subjects will be assessed using the CMH test statistic, stratified by type of XOI, and Screening eCrCl (as appropriate as stated in [Section 9.1](#)). Results will be summarized by randomized treatment group and expressed as proportions and corresponding adjusted 95% CI of the difference between response rates.

The proportion of subjects reporting gout flares will also be summarized at each visit.

The patient-reported outcomes (ie, SDS, WPAI:SHP, and EQ-5D-3L) will be summarized by visit (Visits 3, 6, 9, . . . 24). In addition, the mean score at last on-study visit will be analyzed using analysis of covariance (ANCOVA), which include terms for treatment stratification factors (as appropriate as stated in [Section 9.1](#)) and Baseline patient reported outcome value as covariate.

9.4.5. Interim Analyses

No formal interim analysis is planned.

10. QUALITY CONTROL AND ASSURANCE

Quality assurance and quality control systems will be implemented and maintained with Standard Operating Procedures by the Sponsor and its designee(s), as appropriate, to ensure that this clinical study is conducted and data are generated, documented (recorded), and reported in compliance with the protocol, International Conference on Harmonisation (ICH) E6 Good Clinical Practice (GCP): Consolidated Guidance, and the applicable regulatory requirements.

This study will be monitored by the Sponsor in accordance with GCP, and may be audited or reviewed by an independent Quality Assurance department, EC, and/or regulatory authorities. This implies that monitors and auditors/inspectors will have the right to inspect the study sites at any time during and/or after completion of the study and will have direct access to data/source documents, including the subject's file. By participating in this study, Investigators agree to this requirement.

Measures will be undertaken to protect the confidentiality of records that could identify subjects, respecting the privacy and confidentiality rules in accordance with applicable regulatory requirements.

11. ADMINISTRATIVE CONSIDERATIONS

11.1. Ethics Committee Approval

At a minimum, the following documents must be reviewed and approved by ECs (including IRBs and IECs), as required by local laws and EC requirements, before subjects are screened for entry into the study:

- Study protocol and amendment(s).
- Written Informed Consent Form(s) and consent form updates.
- Subject recruitment procedures (eg, advertisements).
- Written information to be provided to subjects.
- IB and available safety information. Note: ECs do not approve IBs but are responsible for acknowledging receipt.
- Information about payments and compensation available to subjects.

The EC approval must be in writing, clearly identifying the study (by protocol date and/or version), the documents reviewed, including informed consent form, and date of the review. The Investigator has the responsibility to provide the Sponsor with the written EC approval prior to initiating any study-related procedures. The Investigator also has the responsibility to inform the EC of serious and unexpected AEs and protocol deviations, and to provide the EC with a synopsis of the study report upon study completion according to the EC's policy.

11.2. Ethical Conduct of the Study

This study is to be conducted in accordance with the protocol, ICH E6 GCP, and all other applicable regulatory requirements. Investigators must immediately notify the Sponsor or designee (if applicable) of serious breaches in GCP that have occurred at their study site, which are likely to effect to a significant degree (a) the safety or physical or mental integrity of the subjects of the study or (b) the scientific value of the study.

11.3. Subject Information and Consent

Note: all references to "subject" in this section refer to the study subject or his/her legally acceptable representative.

Prior to participation in any study-specific procedures, each subject must sign and date an EC-approved written ICF in a language the subject can understand.

The language in the written information about the study should be as non-technical as practical, and should be understandable to the subject. Before informed consent is obtained, the Investigator should provide the subject ample time and opportunity to inquire about the study and to decide whether or not to participate.

All questions about the study should be answered to the satisfaction of the subject. The written ICF should be signed and personally dated by the subject and by the person who conducted the

informed consent discussion, with any additional signatures obtained as required by applicable local regulations and EC requirements. Each subject will be informed that participation is voluntary and that he/she can withdraw from the study at any time. All subjects will receive a copy of their signed and dated ICF.

11.4. Subject Confidentiality

The collection of personal data for this study will be limited to data that are necessary to investigate the utility of the IP used in this study. These data will be processed with adequate precautions to ensure confidentiality according to local laws.

The Sponsor ensures that the personal data are as follows:

- Collected for a specified and legitimate purpose.
- Processed fairly and lawfully.
- Accurate and up to date.

Explicit consent for the processing of personal data will be obtained prospectively from the participating subject.

The Sponsor, whose responsibilities require access to personal data, agrees to keep the identity of study subjects confidential. This confidentiality will be maintained throughout the complete data processing.

Study subjects will be entitled to request confirmation of the existence of personal data held by the Sponsor and will have the right to rectify erroneous or inaccurate data up until database lock.

11.5. Study Monitoring

The Sponsor will monitor this clinical study through central analysis, on-site monitoring visits, and remote data checks to check the adequacy of site staff and facilities, and to ensure adherence to the protocol, study procedures, and applicable regulations. The site monitor will also assess proper CRF completion and source document retention. The Investigator and study site staff are expected to provide adequate space for monitoring visits and to allocate sufficient time to permit adequate review of the study's progress. The Investigator will permit study-related monitoring, audits, EC review and regulatory inspection(s), providing direct access to source data/documents and study-related facilities (eg, pharmacy, diagnostic laboratories).

11.6. Study Records and Case Report Forms

11.6.1. Study Records and Case Report Forms Records

The Investigator and affiliated institution shall maintain the study documents and records as specified in "Essential Documents for the Conduct of a Clinical Trial" (ICH E6 Section 8), and as required by the applicable regulatory requirement(s). These include, but are not limited to, the protocol, CRFs, AE reports, subject source data (original records or certified copies), correspondence with health authorities and EC, consent forms, Investigator's curriculum vitae, monitor visit logs, laboratory reference ranges and laboratory certification or quality control procedures, and laboratory director curriculum vitae. Subject source data must be maintained as

original records or a certified copy (ie, copy of original information that has been verified, as indicated by a dated signature, as an exact copy having all of the same attributes and information as the original). The Investigator and affiliated institution should take measures to prevent accidental or premature destruction of documents.

Study sites may utilize site-owned electronic medical record systems and/or other computer systems to generate, collect, and store subject source data. When such systems will be used for the study, their use and supporting infrastructure (eg, access/security, written procedures, technical support, and training as applicable) will be identified and documented in site assessment or site visit reports by the Sponsor or designee, and will be reviewed and monitored in accordance with applicable procedures and regulatory requirements. If electronic medical records are maintained (eSource data), the method of verification must be agreed upon between the investigational staff and the Sponsor or designee prior to enrollment of the first subject.

